- **Acceptability** will involve establishing the safety profile of 3 times weekly low dose ferrous sulphate (65mg elemental iron) supplements among deferred prospective blood donors with ID and IDA. This safety profile will be established by comparison to a similar group of participants who do not receive iron supplementation. Participant and key informant views and perspectives of barriers and recommendations for using iron supplementation and nutritional counseling to increase the blood donor pool will also be investigated with participant questionnaires. In addition, focus group discussions and key informant interviews will provide critical insights into the acceptability of this intervention.
- **Key blood donation measures** include haemoglobin levels at 4 months, the change in haemoglobin concentration, ferritin levels at 4 months, the proportion of participants with corrected ID, the proportion of participants who return to the blood centre to donate blood and the proportion of returners who are able to successfully donate (not deferred). In addition, the incidence of ID and IDA among blood donors will be determined using a group of participants who were not deferred, were not ID and did not have IDA at baseline.

To achieve this objective, a pilot study will be conducted for one year. This allows for enrolment over a maximum of 6 months and 6 months of follow-up for the last individual enrolled. The follow-up period incorporates 4 months of the iron supplementation intervention.

Secondary Objectives

- To determine changes in haemoglobin in blood donors over a 6-month period.
- To determine the impact of iron supplementation on the change in haemoglobin.
- To estimate the prevalence of iron deficiency and iron deficiency anaemia in prospective first-time blood donors.
- To determine the factors associated with iron deficiency and iron deficiency anaemia among prospective blood donors.
- To determine the prevalence of malaria or adverse events among the prospective first-time blood donors.
- To identify the barriers and facilitators of repeat donation and the use of dietary and iron supplementation interventions to address iron deficiency and/or anaemia among blood donors.
- To determine feasibility of the intervention, through documenting implementation fidelity, intervention adaptation, and intervention strengths and weaknesses.
- To understand participant and key informant acceptance of the intervention.

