Individuals in blood donor groups will proceed with routine assessment by blood donation staff for eligibility for whole blood donation as defined by the NBSG. As part of this assessment, these potential blood donors will undergo routine semi-quantitative haemoglobin assessment using the copper sulphate (CuSO_4) gravimetric method with a cut- off Hb concentration value of <13.0 g/dL for males and <12.0 g/dL for females. Prospective blood donors who consent and meet the eligibility criteria will be eligible for the study. The site will log potential blood donors who are approached to participate in the study and document whether the participant elects or declines involvement with the study.

- *Consenting Procedure*

Prospective blood donors who pass all pre-donation assessments, and those who are deferred specifically on account of failed CuSO_4 will be approached and informed about the study by trained research assistants. All eligible participants will provide written informed consent and, in the case of minors, additional assent. Eligible enrolled minors who turn 18 during the course of the study will need to be re-consented as adults.

- *Rescreening*

Rescreening will be allowed for previously excluded participants after four months. In this case a new study identification number will be assigned to the participant and the participant will be identified with this new number for the rest of his/her participation in the study. If participant has been enrolled, re-screening is not allowed. In case rescreening occurs, all evaluations re-assessed should meet the eligibility criteria. A new informed consent form (ICF) must be signed only if there is an interruption in the participant's eligibility evaluation and the investigator chooses to re-screen the participant following screen failure. If a new ICF is signed,

AEs and medical history will be assessed relative to the new informed consent date.

- *Blood Sampling:*

Participants who consent/assent to participate will have 5ml of whole blood sampled into an EDTA tube for full blood count, peripheral film comment, malaria rapid test and plasma ferritin analysis. This blood draw will take place prior to donation for those participants who can donate to prevent a classification of ID due to sampling immediately after a donation.

- *Estimation of Iron Deficiency and Iron Deficiency Anaemia*

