## **Objectives**

### **Primary Objectives**

The primary objective of the Iron Supplementation Trial is to determine the potential for an iron supplementation strategy to increase blood donations in Ghana. To determine this potential, the study will investigate the feasibility and acceptability of this intervention along with key return blood donation measures among first-time blood donors found to have low haemoglobin or found to have IDA or be ID within the catchment areas of the SZBC. These aspects of the potential for this intervention will be

operationalized as follows:

- **Feasibility** of recruitment, enrolment, retention, and adherence will be evaluated with a target retention rate > 90% of all participants recruited completing the trial. If we are unable to achieve this target, alternative strategies will be considered for the UH3 phase.
- **Acceptability** will involve establishing the safety profile of 3 times weekly low dose ferrous sulphate (65mg elemental iron) supplements among those assigned to iron supplementation at enrolment. This safety profile will be established by comparison to a similar group of participants who do not receive iron supplementation. Participant and key informant views and perspectives of barriers and recommendations for using iron supplementation and nutritional counselling to increase the blood donor pool will also be investigated with participant questionnaires. In addition, FGDs and key informant interviews will provide critical insights into the acceptability of this intervention.
- **Key blood donation measures** include haemoglobin levels at 4 months, the change in haemoglobin concentration, ferritin levels at 4 months, the proportion of participants with corrected ID, the proportion of participants who return to the blood centre to donate blood and the proportion of returners who are able to successfully donate (not deferred). In addition, the incidence of ID and IDA among blood donors will be determined among those who consent to the Iron Supplementation Trial at screening.

To achieve this objective, a pilot parallel groups trial will be conducted for one year. This allows for enrolment over a maximum of 6 months and 6 months of follow-up for the last individual enrolled. The follow-up period incorporates 4 months of the iron supplementation intervention.

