## **Stratification and Sampling**

The SZBC contributes to the blood service needs of the Western, Central, Greater Accra, Eastern and the Volta Regions of Ghana. In 2018 and 2019, the SZBC attended to an average of 550 prospective voluntary blood donors a week, including 80 walk-in donors. Out of this number, the study will recruit all participants (who fall within the inclusion criteria) reporting per day for up to 6 months until the sample size is attained. Eligible participants will form the sampling frame for the study.

Donors will be informed about the trial and the prevalence study of ID and IDA. Due to a need to recruit approximately equal numbers of participants in the 2 groups in the trial, donors who fail the copper sulphate test will be disproportionately approached for participation. This creates a stratification of donors by status with regard to the outcome of the copper sulphate test. Within these strata the proportion of donors who are ID and IDA will be determined. The estimates of these proportions within strata will be unbiased but if one simply averages over the strata, we expect that the estimates of the proportion who are ID or IDA will have positive bias. However, since we will have estimates of the proportion of donors who fail the copper sulphate test, we can post-stratify the proportions of donors who are ID or IDA by the proportion of donors who fail the copper sulphate test.

Out of the sampling frame, participants will be purposively sampled for FGDs. In all there will be ten FGDs i.e., two groups (male-only and female-only) selected to represent each of the five NBSG voluntary blood donation categories (excluding mass/media event donors), and with each group composed of both first-time and repeat donors. In-depth interviews will also be conducted with blood donation staff and medical officers responsible for blood donation.

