The incidence of ID or IDA will be examined among participants in the control group (who are not ID and do not have IDA at baseline by definition). These estimates will be in the form of events per unit time. The generalized estimating equation (GEE) version of Poisson regression will be used with the robust standard error. A model with just an intercept and an offset (for those without complete follow-up for the final analysis and for interim analyses) will be used to estimate the rate and models with the covariates age and sex will be used to test for sex and age specific differences. Age will be treated as a categorical variable in these models with ranges 17-20, 21-40 and greater than 40. Note that data from different subjects will be treated as independent in this model: GEE are being used here to account for potential overdispersion. The same approach will be used to examine the incidence of ID and IDA separately.

Adherence will be assessed by pill counting and administering adherence questionnaires. Adherence will be calculated as the percent of follow-up days/expected pill consumption days, participant did consume the pill. A similar analysis will be conducted based on dosage if more than 10% of participants have a change in their dosage during follow-up. We will also use a validated simplified self-report medication adherence measure with the following six items:

- Number of remaining pills (integer).
- Ever forgot to take the study medicine (Yes or No).
- Are you careless at times about taking the study medicine (Yes or No).

Sometimes if you feel worse, do you stop taking your study medicine (Yes or No).

How often have you not taken the study medicine in the last week (4 options: 0, 1 day, 2 days, 3 days).

Days missed taking pills in the last two weeks (integer).

These items will be summarized with counts and proportions.

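### The incidence of ID/IDA among blood donors has three different stated populations, and the one analysed mixes deferred with non-deferred controls

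*SAP*

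**What the plan says.** The documents describe the population for one measure, the incidence of ID and IDA, in three ways.

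- **Protocol, Primary Objectives (key blood donation measures):** incidence among blood donors is to be determined "using a group of participants who were not deferred, were not ID and did not have IDA at baseline".
- **SAP 1.2, Primary Objectives:** "the incidence of ID and IDA among blood donors will be determined among those who consent to the Iron Supplementation Trial at screening".
- **SAP 7.2.2, safety and feasibility analyses:** "The incidence of ID or IDA will be examined among participants in the control group". A parenthesis notes that controls are free of ID and IDA at baseline; it does not mention deferral. The protocol's Quantitative Data Analysis section also uses the control group.

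The SAP's rate model is a Poisson GEE with an intercept and an offset. Beyond that, "models with the covariates age and sex will be used to test for sex and age specific differences". There is no term for deferral or donation.

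Three other statements determine who is in the control group. Copper sulphate deferral applies at "<13.0 g/dL for males and <12.0 g/dL for females" (Protocol, Donor Eligibility Screening by NBSG). Both documents form the groups on need for iron, whether or not the person was deferred. And SAP 1.2, Stratification and Sampling, says that "donors who fail the copper sulphate test will be disproportionately approached for participation".

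**The concern.** The protocol objective has three conditions: not deferred, no ID and no IDA. The analysis keeps the last two and drops the first. A control group formed without regard to deferral can include people turned away at screening, and these people are recruited preferentially. The resulting rate is not the one the objective defines, and it would change if recruiters approached more or fewer copper sulphate failures.

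Deferral is plausibly related to this outcome. The protocol's introduction puts the loss from one whole blood donation at almost 250 mg of iron, against female stores of about 300 mg. Its Blood Sampling text places the baseline draw before donation. For a control who donates at screening, that loss therefore falls after the baseline measurement; a deferred control does not incur it then.

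The SAP's objective has a separate problem. People already iron deficient at screening cannot be new cases. Those with Hb below 10 g/dL contribute to the prevalence study but do not enter the trial (SAP 3.4).

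At stake is a secondary descriptive rate with three possible denominators. If this is not settled before database lock, the choice could be made after the results are known.

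**Working it through.** **1. The plan's own figure.** No figure is given for the incidence analysis. The control group's size comes from the trial sample size: SD 1.89, margin 1.0, true difference −0.3, one-sided alpha 0.025, power 85%.

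n per arm = 2 × (1.960 + 1.036)² × 1.89² / (1.0 − 0.3)² = 131. Then 262 / 0.9 = 291.1, rounded up to 292, or 146 per arm. Both stated figures reproduce.

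**2. Who can be a deferred control.** Under the SAP rule (ID, IDA or low haemoglobin go to iron), two kinds remain:

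- women with normal ferritin and Hb between 11.5 and 12.0, if the 11.5 limit of protocol Table 4 defines low haemoglobin;
- people of either sex who failed copper sulphate but whose full blood count (FBC) does not confirm low haemoglobin.

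Under the protocol's Design text (only ID or IDA go to iron), any eligible deferred person without ID is also a control.

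**3. Share of non-anaemic women in the 11.5–12.0 band.** Normal model, SD 1.89; share = [Φ((12.0 − μ)/1.89) − Φ((11.5 − μ)/1.89)] / [1 − Φ((11.5 − μ)/1.89)]. The documents give no female mean. The value 11.5 is implied by the margin illustration (half of donors anaemic); 13.4 is the mean of the West African sample, sexes combined.

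| Assumed female mean (g/dL) | Share in band |
|---|---|
| 11.5 | 20.9% |
| 12.0 | 17.3% |
| 12.5 | 13.9% |
| 13.0 | 10.8% |
| 13.4 | 8.6% |

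This treats ferritin status as unrelated to Hb within the band.

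**4. Share of all controls.** Multiply by the proportion of women among controls, assumed 10% to 50%: from 0.10 × 0.086 = 0.9% to 0.50 × 0.209 = 10.4%. Copper sulphate error and preferential recruitment could raise this; the documents quantify neither.

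**5. Effect on the rate.** Let f be the deferred share of control person-time and RR the rate in deferred relative to non-deferred controls. Then pooled rate / non-deferred rate = 1 − f(1 − RR).

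| f | RR 0.5 | RR 1 | RR 1.5 |
|---|---|---|---|
| 5% | 0.975 | 1.00 | 1.025 |
| 10% | 0.95 | 1.00 | 1.05 |
| 30% | 0.85 | 1.00 | 1.15 |

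The documents give neither f nor RR, so no single figure follows. The pooled rate is too low only if RR is below 1.

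**6. Precision, for scale.** 131 to 146 controls × 0.5 year = 65.5 to 73 person-years. At an assumed 0.2 events per person-year that is 13.1 to 14.6 events. The upper 95% limit exceeds the estimate by exp(1.96/√13.1) − 1 = 72% to exp(1.96/√14.6) − 1 = 67%.

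**The case against.** The strongest defence is that the effect is small and the measure minor. The SAP sends participants with low haemoglobin to iron, which removes most deferred people from the control group. Both documents say that well over half of donors are men, and that fewer than half of donors are likely to be anaemic; both push the share in step 4 towards its lower end. The band may even be empty: the SAP's group rule gives no number for low haemoglobin, and the protocol's severity text puts mild anaemia in women at 11 to 11.9 g/dL, whereas Table 4 uses 11.5. If the limit is 12.0, only unconfirmed copper sulphate failures remain. A shift of a few percent is also well inside the interval in step 6.

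All of this stands as a limit on size. It does not settle which population is meant. It also leaves the dependence on recruitment mix, which the SAP accepts as a problem for prevalence: section 7.1 weights ID and IDA prevalence by deferral stratum for this reason, while incidence gets no such step.

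A reader might go further and infer that the pooled rate will understate incidence after donation. The documents do not support this. Avoiding the iron loss points to a lower rate in deferred controls, but women just above the anaemia limit may develop IDA more often, so the net sign is unknown. The protocol objective says not deferred; it does not say gave blood at screening. A person deferred at screening may also donate during follow-up, when return donation is recorded.

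**Conclusion.** The concern holds as a mismatch of populations. Followed literally, SAP 7.2.2 estimates the rate in a group other than the one the protocol objective defines, and the SAP objective names a third group that includes people already iron deficient. The group analysed can contain deferred participants in a proportion set by recruitment.

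Under the SAP's group rule, the threshold gap alone puts about 1% to 10% of controls in the deferred category. That rests on a normal distribution with SD 1.89, a female mean of 11.5 to 13.4, 10% to 50% women and the 11.5 limit. If these controls had no events at all, the pooled rate would be 1% to 10% too low; if their rate were higher than that of non-deferred controls, it would be too high. Larger distortions need frequent copper sulphate error or strong preferential recruitment, and the documents give no figure for either. Neither a direction nor a single magnitude should be claimed. The primary analysis is not affected.

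**What to change.** 1. In SAP 7.2.2, estimate the headline incidence of ID/IDA in controls who were not deferred at screening, as the protocol objective defines.
2. Report the rate in deferred controls separately, or add screening deferral status to the Poisson model.
3. Align the protocol's Quantitative Data Analysis section and the SAP 1.2 objective with the same population.
4. State the Hb limit behind low haemoglobin in the SAP's group rule and reconcile it with Table 4 and the protocol's severity text, so that the make-up of the control group is clear.

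No new data are needed: the SAP already analyses the copper sulphate result, and the NBSG donor record captures the donation outcome if a split by donation is wanted as well.

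The cost is a smaller denominator. If 10% of control person-time is set aside at an unchanged rate, the standard error of the log rate rises by 1/√0.9 − 1, about 5%; at 30% it rises by 1/√0.7 − 1, about 20%.

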### Additional Analyses

Additional analyses will include longitudinal models for diagnoses of ID, diagnoses of IDA, haemoglobin levels and ferritin levels. The first two outcomes will be treated as binary variable and the latter two will be continuous variables. These models will use GEE to account for the repeat measurements from subjects. A significance level of 0.05 without multiplicity adjustment will be utilized for model interpretation.

Comparison of the results from the copper sulphate test and haemoglobin levels from the FBC will be examined with logistic regression models. These models will model the probability of the copper sulphate test being positive as a function of haemoglobin levels. Models will be fit separately for men and women. Exploratory analyses will investigate if age or factors relating to diet (as listed below) impact the nature of this relationship. The interaction terms between these factors and haemoglobin levels will be added to the model as explanatory variables and the null hypothesis that the regression coefficient associated with the interaction is zero will be tested. Factors relating to diet (responses are obtained from baseline and follow-up questionnaires) include:

Baseline vegetarian status (No, Strict, or Partial).

Number of meals yesterday (4 options: 0, 1, 2, 3 or more).

Frequency of consuming specific foods and beverages category (5 options: daily, weekly, monthly, rarely, never). The foods and beverages categories include fruits and vegetables, meat, poultry, fish, beans and peas, tea/coffee. Each category will be analyzed separately.

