### 3.4 Baseline characteristics

Baseline characteristics for those who enrol in the trial will come from information collected on the screening and enrolment forms. The only characteristics captured for those in the anaemia deferment study are age, sex, if the person has previously donated, and the type of donation (i.e., replacement/family or voluntary). For those in the study of ID/IDA information on abnormal peripheral blood film, malaria, haemoglobin, ferritin, and TTI status will also be obtained. Additional information will be available for those in the trial. For the open report, baseline characteristics will be summarized pooled across the two treatment groups and presented separately for those in the anaemia deferment study, the ID/IDA study, and the trial. Note that these study populations are related as follows: everyone in the trial is in the ID/IDA study, and everyone in the ID/IDA study is in the anaemia deferment study. Note that someone who consents to the trial but is found to have levels of haemoglobin that are too low at screening will participate in the ID/IDA study but will not participate in the trial.

For the closed report, baseline characteristics will be summarized by treatment group for the Iron Supplementation Trial.

The following baseline characteristics will be summarized with counts and percentages for binary and categorical variables, medians and quartiles for continuous variables and ordinal variables when available for each of the 3 components of the study.

Demographics:

- Age: summary as continuous variable.
- Sex.
- First-time donation status (Yes or No).
- Number of children (an integer equal or above 0).
- Marital status (6 options).
- Home situation (6 options).
- Main method of travel (private or public).
- Highest level of education completed (7 options).
- Employment category (8 options).
- Number of expensive, durable consumer items (an integer in the range 0-7).
- Ethnic background (6 options).
- Religion (5 options).

Screening laboratory results:

- Haemoglobin concentration.
- Plasma ferritin concentration.

- Malaria test results from a malaria rapid diagnostic test.
- Abnormal peripheral blood film results reported by type of abnormality (i.e., helminthic infection, malaria, neutrophilia, leucocytosis, and lymphocytosis).
- ID present
- IDA present.

Medical History:

- Diagnoses (19 options, select all that apply).

Nutritional History:

- Number of meals yesterday (4 options).

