## **7 Quantitative Data Analysis**

### **7.1 Cross-sectional study**

Analytical approaches to the analysis of data from the prevalence study will focus on univariate summaries but will also investigate risk factors for deferral. An exact

confidence interval for the probability of deferral will be computed using the method first described by Clopper and Pearson. Logistic regression will be used to assess risk factors for deferral. These risk factors will include age, sex, previous donation status and type of donor.

Since recruitment at donation events focuses on informing individuals who fail the copper sulphate test about the study, we expect that the proportions of those who are ID and IDA will be higher than the proportion among those attending a donation event. For this reason, we will estimate the level of ID and IDA overall by weighting the estimates within deferral strata by the observed probability of deferral based on the cross-sectional study of deferral (but restricted to first time donors, or voluntary first time donors depending on who enrolls into the ID/IDA study). To obtain 95% confidence intervals for the overall proportion of those who are ID and IDA we will use a Bayesian approach in which we sample the probability that first-time donors are deferred for low haemoglobin from its posterior distribution (which is a beta distribution) and we sample the probability of being ID and IDA conditional on deferral status from their posterior distributions (which will also be beta distributions). We can then combine these draws from the posterior distributions to obtain weighted estimates of the probability of being ID and IDA that will be consistent for these probabilities in the overall population. Risk factors for being ID and IDA conditional on the outcome of the copper sulphate test will be examined using logistic regression.

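### The copper sulphate model is fitted, uncorrected, to a sample enriched for copper sulphate failures, so its fitted failure probabilities (not its haemoglobin slope) are biased upward

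*SAP*

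**What the plan says.** Comparing haemoglobin by copper sulphate with haemoglobin by the automated analyser is a listed secondary objective in both documents. The analysis is in SAP 7.2.2, Additional Analyses: "These models will model the probability of the copper sulphate test being positive as a function of haemoglobin levels". It continues: "Models will be fit separately for men and women". Age and diet factors are then examined through their interactions with haemoglobin. The protocol's Quantitative Data Analysis section gives the same model. I read a positive test as a failed one.

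On recruitment, SAP 1.2 (Stratification and Sampling) gives the reason, "Due to a need to recruit approximately equal numbers of participants in the 2 groups in the trial", and the consequence: "donors who fail the copper sulphate test will be disproportionately approached for participation". SAP 7.1 repeats that "recruitment at donation events focuses on informing individuals who fail the copper sulphate test about the study".

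On who has an analyser value, the protocol (Blood Sampling) says: "Participants who consent/assent to participate will have 5ml of whole blood sampled into an EDTA tube for full blood count". The unselected deferral cohort has none. SAP 3.4 says: "The only characteristics captured for those in the anaemia deferment study are age, sex", and adds only previous donation and type of donation.

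For overall ID and IDA prevalence the SAP deals with this selection by "weighting the estimates within deferral strata by the observed probability of deferral based on the cross-sectional study of deferral", restricted to first-time donors. For ID and IDA risk factors it conditions on the copper sulphate result. Neither approach is carried to the copper sulphate model. The inverse probability weighting in SAP 7.2.3 models membership of the iron group, not sampling, and covers only the primary and efficacy outcomes.

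**The concern.** The copper sulphate result is both the response in this model and the variable on which donors were recruited. SAP 1.2 already expects simply averaged ID and IDA proportions to be biased upward by this recruitment. The same enrichment acts more directly here, because the selection variable is itself the outcome.

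What is at stake is the absolute reading of the curve: how often a donor with a given analyser haemoglobin fails copper sulphate, and whether the test switches near its nominal 13.0 g/dL for men and 12.0 g/dL for women. An uncorrected curve would show donors failing above the true switching point. It could suggest needless deferral that is partly a product of recruitment.

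**Working it through.** The plan gives no figure for this analysis, so there is none to reproduce.

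**Inputs**
- Response, predictor and separate fits by sex: SAP 7.2.2.
- Enrichment for failures: SAP 1.2 and 7.1.
- Haemoglobin SD 1.89 g/dL (simulation only): SAP 2.4.
- Failing share among first-time donors, q: not given. SAP 1.2 expects fewer than half of donors to be anaemic. I use 0.2 to 0.5.
- Failing share in the sample, s: not given. I assume 0.5.
- Slope b, in log-odds of failing per g/dL fall in haemoglobin: not given. I use 1.5 and 5.

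**Formula.** Let f1 and f0 be the probabilities that a failing and a passing donor enter the sample. If entry depends on the result and not otherwise on haemoglobin, then

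odds(fail | Hb, sampled) = odds(fail | Hb) × f1/f0, where f1/f0 = [s/(1−s)] / [q/(1−q)].

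The multiplier does not involve haemoglobin. The slope and the haemoglobin interactions are therefore preserved, and the intercept shifts by logit(s) − logit(q). The haemoglobin at which half fail moves up by that shift divided by b.

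**Numbers.** For q = 0.2: f1/f0 = 1/(0.2/0.8) = 4.0 and ln 4.0 = 1.39. A true failure probability of 0.50 is fitted as 4/(1+4) = 0.80. A true 0.10 has odds 1/9; multiplied by 4 this is 0.444, fitted as 0.444/1.444 = 0.31. The 50% point moves by 1.386/1.5 = 0.92 g/dL or 1.386/5 = 0.28 g/dL. The other rows follow in the same way, from unrounded shifts.

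| q (s = 0.5) | f1/f0 | Intercept shift | True 0.50 fitted as | True 0.10 fitted as | 50% point, b = 1.5 (g/dL) | 50% point, b = 5 (g/dL) |
|---|---|---|---|---|---|---|
| 0.2 | 4.0 | 1.39 | 0.80 | 0.31 | +0.92 | +0.28 |
| 0.3 | 2.3 | 0.85 | 0.70 | 0.21 | +0.56 | +0.17 |
| 0.4 | 1.5 | 0.41 | 0.60 | 0.14 | +0.27 | +0.08 |
| 0.5 | 1.0 | 0 | 0.50 | 0.10 | 0 | 0 |

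**Simulation.** A large-sample simulation used Hb SD 1.89 g/dL, a true 50% point of 13.0 g/dL, half the sample failing, q from 0.1 to 0.4 and slopes of 1.5, 3 and 5 (12 scenarios). At q = 0.2 and slope 3, the unweighted fit recovered the slope (3.01), put the 50% point at 13.46 g/dL (formula: 13 + 1.386/3 = 13.46) and gave a failure probability of 0.80 at 13.0 g/dL. Weighting each result back to its population share returned the 50% point to 13.00 g/dL in that scenario and to between 12.98 and 13.01 across all 12. Restricting the unweighted fit to Hb of at least 10 g/dL changed neither the slope nor the 50% point.

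**The case against.** The strongest reply is that the affected quantities are not named outputs. SAP 7.2.2 promises logistic models and tests of haemoglobin-by-age and haemoglobin-by-diet interactions. It mentions no cut-off, no 50% point and no table of failure probabilities, and the tests it does name remain valid. This stands, and it limits the point to absolute quantities. It does not remove the point, because the stated target is a probability, and the slope alone cannot show whether the test switches at its nominal threshold.

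The second reply is that the size is assumed. That also stands. Equal trial groups do not imply that half the sample fails copper sulphate: groups are set by anaemia, ID or IDA, and an iron-deficient donor without anaemia can pass. Table 1 of the SAP runs from 0.2 to 0.6. With s held at 0.5, q = 0.5 gives no shift and q = 0.6 gives ln[1/(0.6/0.4)] = −0.41. That last case contradicts the planned over-sampling of failures, so it shows only that s cannot be fixed at 0.5 over the whole range. The 33–53% in the protocol's Problem Statement cannot stand in for q, since it is the low-haemoglobin share among deferred donors.

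Third, the pre-donation assessment and a full blood count are both scheduled again at week 24 (SAP Appendix A), and the SAP does not say whether those pairs enter the model. Participants were not recruited on that later result, so a correction built on screening would not carry over to it.

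A reader might infer that the whole method comparison is invalid, or that the SAP commits itself to a wrong cut-off. The documents support neither: the slope, the odds ratio per g/dL and the interaction tests survive, and no cut-off is promised.

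**Conclusion.** The point holds in limited form. Given the SAP's stated recruitment, an unweighted fit to screening pairs overstates the probability of failing copper sulphate at every haemoglobin level, and moves any cut-off read from the curve upward. The direction follows from the planned enrichment. The magnitude does not: the range of 0.08 to 0.92 g/dL for the 50% point rests on an assumed half of the sample failing, 20% to 40% of donors failing, and slopes between 1.5 and 5 per g/dL, and it falls to zero if the two shares agree. Validity of the slope and interactions rests on the logistic form, and on recruitment depending on the copper sulphate result without otherwise distorting the relation with haemoglobin. This is a minor correction to one secondary analysis. It does not bear on the primary endpoint, the safety comparisons or the prevalence estimates.

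**What to change.** State in SAP 7.2.2 which pairs are modelled. For screening pairs, fit each sex's model with inverse-sampling weights and robust standard errors: q/s for donors who fail and (1−q)/(1−s) for donors who pass. Here s is that sex's failing share among the consenting donors with a full blood count, taken before the Hb < 10 g/dL trial exclusion. q is the observed failure proportion for that sex among first-time donors in the deferral study, or among voluntary first-time donors if only they enrol. Equivalently, include logit(s) − logit(q) as a fixed offset and leave it out when predicting. Base every reported failure probability and cut-off on the corrected fit. Do not apply the screening weights to week-24 copper sulphate results; analyse those separately if they are used.

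The cost is a short change to the SAP and one new variable. SAP 7.1 does not already supply it: that section combines posterior draws of stratum proportions and forms no participant-level or sex-specific weight. Sex and previous donation are recorded in the deferral study, so no new data are needed. Intervals will be slightly wider.
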